# 4.3 Exploratory Objectives

- Examine whether any association between prior vaccination and immune response to 2019-20 vaccination is mediated by antibodies to the prior vaccine strains
- Gather information on any adverse events following vaccination
- Characterize humoral immune responses as measured by HI, MN titers, and other
  appropriate humoral immunity assays among subsets of enrollees of particular interest
  due to their age or demographic characteristics, health status, and/or occupational roles
  and responsibilities.

# 5. STUDY ENDPOINTS

# **5.1 Primary Endpoints**

The primary endpoints will be assessed by the following laboratory tests. The choice of laboratory assay may depend in part on how the 2019-2020 vaccine components and circulating strains affect which laboratory assay is most effective in assessing specific antigens.

- HI and/or MN responses to *egg*-grown vaccine reference viruses for all vaccine viruses for each study season at approximately 28 days, including the following endpoints
  - o Seroconversion rate (SCR) defined as the proportion of participants with paired samples that achieved ≥4-fold rises comparing post- versus pre-vaccination titers
  - Geometric mean titers (GMT) and the ratio of post-vaccination titers between the two vaccines (post-vaccination GMT ratio);
  - Geometric mean-fold rise (GMR) defined as the ratio of the post-vaccination titer
     value to the pre-vaccination value
  - o Elevated post-vaccination titers at thresholds greater than 1:40, 1:80, 1:160
- MN responses to the *cell*-grown influenza A/H3N2 (using MDCK-SIAT or other appropriate cell line) vaccine reference viruses at approximately 28 days postvaccination, including the following endpoints:
  - o SCR, post-vaccination GMT ratio, GMR, and elevated post-vaccination titers

## 5.2 Secondary Endpoints

• HI responses to *egg*-grown influenza A/H3N2 vaccine reference viruses at approximately 28 days, including the following endpoints: SCR, post-vaccination GMT ratio, GMR, and elevated post-vaccination titers

## **5.3 Exploratory Endpoints**

- HI and/or MN responses to *cell*-grown *wild-type* influenza viruses at approximately 28 days (if appropriate), including the following endpoints
  - o SCR, post-vaccination GMT ratio, GMR, and elevated post-vaccination titers
  - o SCR, post-vaccination GMT ratio, and GMR as measured by MN, as appropriate
- GMT as measured by NAI pre- and post-vaccination.
- Indicators of immune response to vaccination based on other immunologic assays not listed above (as appropriate)

## 6. METHODS

## 6.1 Overview of Study Design

This is a randomized, single-blind study design. Starting in July 2019, approximately 550 to 700 HCP from two hospitals (275-350 per hospital site) in Israel will be enrolled. Following completion of a written consent form, participants will complete an enrollment survey and grant permission for review of information collected during the SHIRI study, including vaccination status and immune response during the SHIRI study years. Participants will complete an enrollment survey and grant permission to include and integrate information collected during the SHIRI study into the current study's data, including health history, influenza vaccination history, and immune response to vaccination during the SHIRI study years. HCP will be randomly assigned 1:1 to receive a single dose of IIV4 licensed in Israel (expected to be Vaxigrip® Quadrivalent, 15µg of HA per strain) or RIV4 (Flublok® Quadrivalent by Sanofi Pasteur, 45µg of HA per strain) during August-October of 2019. Participants will be blinded to the vaccine that they vaccine, but study staff will be aware of the vaccine. Adverse events following vaccination will be monitored and documented. Blood specimens will be collected prior to vaccination and approximately 28 days after to evaluate immune responses to vaccination.

Eligible HCP who were already vaccinated with Vaxigrip, the vaccine that is routinely available in Israel, at the time they are approached to join the study, will be invited to join the study as part of the Vaxigrip arm. Like randomized participants, participants who were vaccinated with Vaxigrip outside the study will complete a written consent form, an enrollment survey and grant permission for review of information collected during the SHIRI study, including vaccination status and immune response during the SHIRI study years. As part of the consent form, participants will record the estimated date that they received the vaccine, and the location, and will authorize study staff to verify the date of current-year Vaxigrip vaccination in the Clalit EMR and with the hospital vaccination staff. Participants will complete an enrollment survey and grant permission to include and integrate information collected during the SHIRI study into the current study's data, including health history, influenza vaccination history, and immune response to vaccination during the SHIRI study years. Blood specimens will be collected approximately 28 days after to evaluate immune responses to vaccination.

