#### 1. PROJECT SUMMARY

Healthcare personnel (HCP) are believed to be at increased risk of influenza virus infection due to a higher rate of exposure compared with the general population. Close contact with patients may further result in transmission to patients. Vaccination is the most effective method of preventing influenza, but there is limited information on the effectiveness of influenza vaccines among HCP. Some studies have demonstrated reduced influenza vaccine immunogenicity and effectiveness among persons with a history of frequent influenza vaccination, emphasizing the need to examine influenza vaccine effects among HCP who may be frequently vaccinated or demonstrate a high baseline immune response to influenza viruses.

The primary objective of the study is to compare humoral immune responses to a single dose of recombinant hemagglutinin quadrivalent influenza vaccines (RIV4) or to standard egg-

based unadjuvanted quadrivalent influenza vaccines (IIV4) among  $HCP \ge 18$  years old who were vaccinated in the 2018-19 season with IIV4. The trial will be conducted at two hospital sites in Israel during the upcoming influenza season (2019-20) among HCP who were enrolled in the Study of Healthcare Personnel with Influenza and other Respiratory Viruses in Israel (SHIRI).

The study design is a randomized, single-blind, trial. During the study, eligible HCP at each site who consent to participate will be randomized 1:1 to receive a single dose of RIV4 (Flublok™ Quadrivalent by Sanofi, Inc., 45µg of HA per strain) versus a single dose of IIV4 (VaxigripTetra™ by Sanofi, Inc., 15µg of HA per strain). Participants will be blinded to the vaccine that they receive; study staff will not be blinded. Eligible HCP who report already having been vaccinated with Vaxigrip at the time they are approached to join the study will be eligible to participate. All randomized participants will have blood collected just prior to vaccination; all participants, including those who were vaccinated with Vaxigrip outside of the study, will have blood collected , approximately 28 days after to evaluate humoral immune responses to vaccination. Relative efficacy of single doses of study vaccines will be assessed by comparing immunologic responses to vaccination among participants receiving RIV4 and those receiving IIV4. In addition, the effect of prior vaccination in potentially modifying antibody immune responses to vaccine will be evaluated.

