### Inclusion criteria:

- 1. Aged ≥18
- 2. Are currently a member of Clalit Health Services
- 3. Consent to randomized receipt of influenza vaccination with either RIV4 or IIV4, or, if already vaccinated in the current year outside of the study, consent to receive a post-vaccination blood draw
- 4. HCP Group One participation criteria:
  - Participated in the SHIRI study and received influenza vaccination during the
     2018-19 influenza season
- 5. HCP Group Two participation criteria:
  - Participated in any year of the SHIRI study and had PCR-confirmed influenza virus infection during any of the three study years;
- 6. HCP Group One Supplemental criteria:
  - Participated in any year of the SHIRI study, not vaccinated in 2018-2019, but vaccinated in at least one study year;
  - Participated in the SHIRI study during all three years, regardless of vaccination status

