## Exclusion criteria

- 1. Already received an influenza vaccine during the current influenza season
- 2. Not willing or able to get the flu vaccines being used in this study;
- 3. Previous hypersensitivity reaction to the study vaccines, or any vaccine, as reported by the subject
- 4. Received any non-influenza vaccine (e.g., Hepatitis B or other vaccine recommended for HCP) in the 4 weeks prior to the first study visit or plans to receive a vaccine in the 4 weeks following the first study visit
- 5. Currently participating in a study that involves an experimental agent (vaccine, drug, biologic, device, blood product, or medication), or has received an experimental agent within 1 month prior to enrollment in this study, or expects to receive an experimental agent during participation in this study.
- 6. Any condition or employment status that the potential participant or local study site principle investigator (PI) believes may interfere with successful completion of the study prior to December 2019, including being currently pregnant.

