#### 6.3.4 Randomization

Using the list of HCP consented to participate in the study, HCP will be randomized 1:1 to receive one 0.5 mL intramuscular dose of Flublok® Quadrivalent or Vaxigrip Quadrivalent. Randomization lists will be generated by the epidemiologist and data analyst using block randomization to ensure equal sample size in each group.

Randomization will be conducted after enrollment is completed. Randomization will occur separately for participants in Group One and Group Two.

Randomization will not occur for enrolled participants who were vaccinated with Vaxigrip outside of the study.

# 6.4 Study visit 1

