### 6.4.1 Pre-vaccination Questionnaire

All study participants, except those who were already vaccinated outside of the study, will complete a second brief questionnaire to determine whether they are currently experiencing fever, decreased energy, muscle aches, headache, or nausea, and will be asked to rate the subjective severity of any symptom(s) as mild, moderate, or severe (Appendix E. Prevaccination Questionnaire/Vaccine Administration Form). Appendix E will also readdress the study exclusion criteria. Participants reporting subjective fever (of any severity) and those reporting no fever but one or more symptom of moderate or severe subjective severity will not receive study vaccine until their illness has resolved. In this case, a follow up appointment will be made after resolution of the illness, at which time the participant will receive the vaccine. Study number assignment and pre-vaccination blood draw will take place on the day of vaccine administration.

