#### 6.4.2 Blood Draw

All study participants will have 20 ml of venous blood drawn for serologic testing at the first study visit via venipuncture in multiple serum separator tubes with clot activator and gel, according to CDC guidelines. The use of a butterfly needle connected to a vacutainer tube is recommended as the best collection method to minimize hemolysis and to reduce the risk of needle stick injury. As an alternative, the use of a safety needle that connects directly to the vacutainer tube is acceptable. Study staff will document the blood collection in **Appendix F1: Blood Specimen Collection/Tracking Form.** 

Study participants who were vaccinated with Vaxigrip outside of the study will not receive a blood draw during the initial study visit. For these participants, the end-of-season blood draw from SHIRI, which was taken at the end of the 2018-2019 influenza season, will be used as their "pre-vaccination" or "baseline" blood draw.

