### 7.2 Specimen Testing

Assessment of humoral or serologic immune response to antigens that match influenza virus strains that are components of the vaccines and circulating during the study period typically require multiple laboratory assays. We expect that primary methodologies for this effort will be the HI and MN assay. In recent years, MN assays have been required to assess response to cell-grown A/H3N2 viruses, which are a better match to circulating strains and vaccine strains in vaccines that do not involve egg-based production, such as Flublok. Nonetheless, the combination of assays and antigens most relevant to the study objectives will depend on vaccine components, circulating strains, and performance of assays during the study period.

Additional advance serologic assays on a subgroup of specimens may be required. For example, to examine the extent of narrow vs. broad antibody responses and the potential overfocusing of response on specific antibody sites, it may be necessary to quantify inhibition by serum of antigenic site-specific monoclonal antibodies (mAbs) to HA. Response to the two vaccine types may also differ in the extent "back boosting" of antibodies to historical vaccine and circulating viruses as measured by conducting an antibody landscape.

Sera will be tested by HI and MN to measure antibody titers against cell-grown and egg-grown vaccine reference viruses at approximately 28 days post-vaccination compared to baseline samples drawn at day 0 prior to vaccination during each study season. Sera may also be tested by HI and MN against cell-grown wild-type influenza strains, as appropriate. MDCK-SIAT cells or another appropriate cell line will be used to cultivate cell-grown virus strains. A subset of sera from each study arm may also be tested by other immunologic assays as appropriate to measure activity against antigens represented in the study vaccines at day 0 and at approximately 28 days at each site.

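### Externally vaccinated HCP join the IIV4 arm unrandomised and with an older baseline serum, and section 9.2 does not say whether they enter the primary comparison

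*Combined protocol and SAP*

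**What the plan says.** Section 6.1 states that HCP who already have Vaxigrip when approached "will be invited to join the study as part of the Vaxigrip arm". Section 6.3.4 adds: "Randomization will not occur for enrolled participants who were vaccinated with Vaxigrip outside of the study". No corresponding route leads into the RIV4 arm.

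The two kinds of IIV4 participant have different baselines. For those randomised, section 6.4.1 says: "Study number assignment and pre-vaccination blood draw will take place on the day of vaccine administration". For those vaccinated elsewhere, section 6.4.2 says that "the end-of-season blood draw from SHIRI, which was taken at the end of the 2018-2019 influenza season, will be used as their" baseline sample. Section 7.2 knows only "baseline samples drawn at day 0 prior to vaccination", and the primary-objective paragraph of section 9.2 likewise gives baseline as day 0, with no exception.

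On the analysis, section 1 describes the comparison as "comparing immunologic responses to vaccination among participants receiving RIV4 and those receiving IIV4". Section 9.2 compares SCR between vaccine groups by an unadjusted chi-square or Fisher test and calls the primary analyses intention-to-treat. It does not define that set and does not mention the externally vaccinated HCP.

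The eligibility text in section 6.3.1 conflicts on the same people. Inclusion criterion 3 admits them: "if already vaccinated in the current year outside of the study, consent to receive a post-vaccination blood draw". Exclusion criterion 1 bars them without exception: "Already received an influenza vaccine during the current influenza season".

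**The concern.** Two analysts following this text could build different primary datasets. One, reading intention-to-treat in its usual sense, would leave out people who were never randomised. The other, following sections 6.1 and 6.4.2, would count them in the IIV4 arm with a paired sample. The choice would then be made with data in hand.

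Under the second reading, two problems arise in one arm only:

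- **Baseline.** SCR and GMR, two of the four primary parameters, divide by the pre-vaccination titre. A serum from the end of the previous season is not the same quantity as a day-0 serum.
- **Selection.** All four parameters, including the post-vaccination GMT ratio and the titre thresholds, are exposed, because these people chose early vaccination and were not allocated to it. They also know which vaccine they had.

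The bias can go either way. If titres fall between season end and vaccination, the older serum overstates baseline, lowers the apparent IIV4 response and favours RIV4. If these people respond better than the randomised IIV4 recipients, a real RIV4 advantage is diluted.

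**Working it through.** **Plan's own figure.** Table 2 in section 9.1 gives 540 in total for 40% vs 52% (30% relative increase), two-sided 0.05, 80% power. Per arm: [1.96·√(2·0.46·0.54) + 0.842·√(0.40·0.60 + 0.52·0.48)]² / 0.12² = 269.6, so 270, and 540 in total. It reproduces, so the same normal approximation is used below.

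**Inputs from the documents.** Group One target 440 (section 6.3.2); 5% dropout (section 9.1), so 440 × 0.95 = 418 evaluable; 1:1 randomisation; SCR 40% for IIV4.

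**Assumptions, not in the documents.** Log2 fold rise is normal with SD 1.5. True SCR on a day-0 baseline is 40% for both vaccines. External HCP are a share f of the IIV4 arm, f = 5 to 30%. Their older serum overstates baseline by 0, 0.5 or 1.0 log2 units (no drop, 1.4-fold, 2-fold).

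**Step 1, SCR in external HCP.** P(rise ≥ 2 log2) = 0.40 gives a mean rise of 2 − 1.5 × 0.2533 = 1.62. Overstating baseline by 0.5 gives P(Z ≥ (0.38 + 0.5)/1.5) = 0.279. Overstating it by 1.0 gives P(Z ≥ 1.38/1.5) = 0.179.

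**Step 2, arms.** IIV4 n = 418/(2 − f), and RIV4 n is the remainder. IIV4 SCR = (1 − f) × 0.40 + f × external SCR. At f = 20% and a 2-fold drop, the arms are 232 and 186, and IIV4 SCR = 0.8 × 0.40 + 0.2 × 0.179 = 0.356.

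**Step 3, rejection rate.** For SCR, a pooled two-sided z-test against 0.40, counting both tails. For GMR, the false difference in mean log2 rise is f × shift, and the IIV4 variance is 1.5² + f(1 − f) × shift².

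| External share of IIV4 arm | IIV4 / RIV4 n | SCR type I error, 1.4-fold | SCR, 2-fold | GMR, 1.4-fold | GMR, 2-fold |
|---|---|---|---|---|---|
| 5% | 214 / 204 | 5.2% | 5.6% | 5.3% | 6.3% |
| 10% | 220 / 198 | 5.7% | 7.5% | 6.3% | 10% |
| 20% | 232 / 186 | 8.0% | 15% | 10% | 27% |
| 30% | 246 / 172 | 11.8% | 29% | 17% | 51% |

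With no drop and no difference in response, the error is 5.0% at every share.

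**Step 4, opposite direction.** If external HCP had an SCR of 60% at f = 20%, IIV4 SCR = 0.8 × 0.40 + 0.2 × 0.60 = 0.44. A true 40% vs 52% then reads as 44% vs 52%, and power is 37% instead of 69%.

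**Cross-check without the titre model.** Take external HCP as 20% of Group One, which is 84 of 251, or 33% of the IIV4 arm. Set their SCR directly. At 30% the type I error is 10.6%, in favour of RIV4. At 50% it is 10.3%, with the bias reversed. At 40% it is 5%.

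**The case against.** The best counter-argument is that the analysis text leans towards exclusion. Section 9.2 says intention-to-treat, gives baseline as day 0 and, under the secondary objectives, relies on randomisation to remove confounding. External HCP meet none of these conditions. The summary sentence in section 1 may be generic wording, not an as-treated rule. On this reading they are enrolled as an extra cohort, which is a legitimate choice, and the only defect is an undefined term.

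That does not settle the point. Section 6.1 places them in the arm and section 6.4.2 gives them a baseline, which serves little purpose unless they are analysed for response. Section 9.2 defines SCR on participants with paired samples, which they would then have.

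The limits on the numbers do stand. The external share, the titre drop, the SD and the 60% are all assumed. Enrolment starts in July and study vaccination runs from August to October, so the share may be modest, although no cap is stated. The model treats titres as continuous and applies only the 4-fold rule, while the opening of section 9.2 also requires a post-vaccination titre of at least 1:40. The larger entries in the table are corner cases.

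**Conclusion.** The concern holds. The text leaves the primary analysis population undetermined. Followed literally, sections 6.1 and 6.4.2 put non-randomised people with a different baseline into one arm of an unadjusted comparison. This rests on the wording and is certain; the bias is conditional. It is nil if there is neither a titre drop nor a difference in response. With a titre drop alone and external shares of 5 to 10% of the IIV4 arm, it is small for SCR (5.2 to 7.5%). At 20 to 30% it is material: 8 to 29% for SCR and 10 to 51% for GMR, under the assumptions above. It must be fixed because the analysis set should be settled before the data are seen and because the remedy is mostly wording.

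**What to change.** - In section 9.2, define the primary intention-to-treat set as randomised participants only, with a day-0 serum required for SCR and GMR.
- Report externally vaccinated HCP separately, as an observational cohort or in a labelled sensitivity analysis.
- Amend the phrase in section 6.1 that places them in the Vaxigrip arm, and align the comparison sentence in section 1.
- Reconcile inclusion criterion 3 with exclusion criterion 1 in section 6.3.1.
- State power on the number randomised, and say that external HCP do not count towards it.

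**Cost.** There are fewer IIV4 observations in the primary test. On the same scale as the table, if external HCP are 10/20/30% of the IIV4 arm and are not replaced, about 198/186/172 evaluable randomised HCP remain per arm. Power for 40% vs 52% is then about 67/64/61% instead of 69%.

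If they instead fill 10/20/30% of the whole Group One target (44/88/132 of 440), then 396/352/308 are randomised, or 188/167/146 evaluable per arm, and power is about 65/60/54%. Keeping 440 randomised means recruiting those 44/88/132 in addition.

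The starting 69% is below the planned 80% because 440, less dropout, is fewer than the 540 in Table 2. That is a separate matter and not a cost of this change.

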# **6.2 Study Setting and Source Population**

This study will be conducted among HCP who were enrolled in SHIRI for at least one year. SHIRI was conducted during the 2016-2017, 2017-2018, and 2018-2019 influenza seasons at the following two hospitals:

Beilinson Hospital, Rabin Medical Center, Petah Tikva, Israel Soroka Medical Center, Beersheva, Israel

## 6.3 Participant Identification and Recruitment

Consent, screening, enrollment, and all study visits will take place at designated study site locations.

#### 6.3.1 Inclusion and Exclusion Criteria

The following inclusion and exclusion criteria will be applied to determine eligibility for enrollment.

### Inclusion criteria:

- 1. Aged ≥18
- 2. Are currently a member of Clalit Health Services
- 3. Consent to randomized receipt of influenza vaccination with either RIV4 or IIV4, or, if already vaccinated in the current year outside of the study, consent to receive a post-vaccination blood draw
- 4. HCP Group One participation criteria:
  - Participated in the SHIRI study and received influenza vaccination during the
     2018-19 influenza season
- 5. HCP Group Two participation criteria:
  - Participated in any year of the SHIRI study and had PCR-confirmed influenza virus infection during any of the three study years;
- 6. HCP Group One Supplemental criteria:
  - Participated in any year of the SHIRI study, not vaccinated in 2018-2019, but vaccinated in at least one study year;
  - Participated in the SHIRI study during all three years, regardless of vaccination status

